1.0 Objectives

1.1 Study Objectives

Describe the purpose, specific aims or objectives. State the hypotheses to be tested.

Aim 1: To add a cardiovascular health (CVH) module to the existing perinatal home visitation program delivered by Nurse Family Partnership (NFP) visiting nurses in the Northern Appalachian region of Central Pennsylvania.

Aim 2: To train selected NFP visiting nurses on the CVH module and assess the acceptability of the module as well as the fidelity of delivery to pregnant and postpartum women.

Aim 3: To demonstrate the feasibility of enrolling and following pregnant women participating in the NFP program into a pilot research study evaluating a CVH module delivered as part of the existing NFP program.

Aim 4: To develop an activity protocol during and after pregnancy to decrease sedentary behavior during and after pregnancy and increase activity level during the postpartum period.

Aim 5: To pilot the use of digital devices to encourage and monitor activity and associated biometric outcomes, primarily blood pressure and actigraphy.

1.2 Primary Study Endpoints

State the primary endpoints to be measured in the study.

Clinical trials typically have a primary objective or endpoint. Additional objectives and endpoints are secondary. The endpoints (or outcomes), determined for each study subject, are the quantitative measurements required by the objectives. Measuring the selected endpoints is the goal of a trial (examples: response rate and survival).

- Successful integration of CVH modules into NFP program during pregnancy and up to 6 months after delivery.
- Good acceptability of the CVH module by NFP visiting nurses and participants.
- Successful consent of 20 pregnant women into pilot study.

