Digital devices to track human health have become widely utilized both by individuals and in medical care. The sophistication, ease of use, accuracy and cost have improved dramatically in recent years. Continuous glucose monitoring has become the standard for managing patients with type 1 diabetes with immediate data access (now through the cloud) by caregivers to guide treatment doses and regimen.⁷³ We pioneered the use of continuous glucose monitoring during pregnancy in women with polycystic ovary syndrome and documented good correlations with concurrently conducted oral glucose tolerance tests in a cohort of women across four time points in pregnancy.⁷⁴ Such devices are ideal for prenatal care where biometric factors as maternal weight, maternal blood pressure and fetal heart rate are important prognostic factors for the pregnancy outcome and maternal and child health. All of these factors can be accurately tracked by digital devices and our team has had both extensive clinical and research experience utilizing them. The most important of these biometric factors is maternal blood pressure, as increases are suggestive of gestational hypertensive disorders. Elevated blood pressure is arguably the greatest risk factor for serious maternal morbidity and mortality through pre-eclampsia or eclampsia. Ambulatory Blood Pressure Monitoring (ABPM) has been studied extensively not only during pregnancy^{75,76} but for a number of cardiovascular conditions and has been found to correlate well with measures obtained in medical⁷⁷ settings and to correlate well with response to treatment and risk of cardiovascular events.⁷⁸ We have used 24 hour ABPM in a cohort study of women at risk for developing gestational hypertension throughout pregnancy (N = 73).⁷⁹ We found strong and significant correlation between measurements obtained through ABPM and those in the clinic. Further the strongest correlation was in those with the least risk, the population we are proposing to study in this proposal. Our results have been validated in meta-analyses of home blood pressure monitoring (HBPM), intermittent self-measurement of BP outside of a clinic setting) during pregnancy though most studies have used it in at risk populations to augment clinical measurements, instead of in lieu of clinical measurements as we are proposing.^{76,80} Meta-analysis has shown the use of HBPM is associated with significantly fewer antepartum visits, diagnoses of pre-eclampsia, pre-delivery hospital admissions and inductions with no difference in maternal and neonatal morbidity and mortality.^{76,80} Recently two large multi-center randomized controlled studies of AHBPM in pregnancy in an at risk population for gestational hypertensive disorders found no benefit in AHBPM in diagnosing such disorders earlier than the control clinic based population (BUMP 1)⁸¹ nor any benefit in AHBPM in reducing systolic blood pressure (BUMP 2).⁸² Our study will use periodic HBPM, to monitor all patients (many patients who develop these disorders have no risk factors) during pregnancy. This study will also monitor blood pressure across the transition from pregnancy to postpartum which will provide novel data about this understudied transition. Additionally, we will monitor steps with an accelerometer and movement/sleep with an actigraphy device as we have done in previous lifestyle intervention studies.

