4.2 Recruitment process

Describe how potential subjects first learn about this research opportunity or indicate as not applicable if subjects will not be prospectively recruited to participant in the research. Subject recruitment can involve various methods (e.g., approaching potential subjects in person, contacting potential subjects via email, letters, telephone, ResearchMatch, or advertising to a general public via flyers, websites, StudyFinder, newspaper, television, and radio etc.). **DO NOT** include the actual recruitment material or wording in this protocol.

[Do not type here]

4.2.1 How potential subjects will be recruited.

Potential participants will be recruited through established partnerships with Geisinger and UPMC Nurse Family Partnership agencies. After potential participants are identified by visiting nurses and/or their supervisors, visiting nurses will share information about the pilot study verbally and through a written summary handout prepared by the study team.

4.2.2 Where potential subjects will be recruited.

Potential participants will be recruited in their own homes during regularly scheduled home visits with their NFP visiting nurse.

4.2.3 When potential subjects will be recruited.

Potential participants will be recruited during pregnancy (<28 weeks' gestation) during regularly scheduled home visits with their visiting nurse from NFP.

4.2.4 Describe the eligibility screening process and indicate whether the screening process will occur before or after obtaining informed consent. Screening begins when the investigator obtains information about or from a prospective participant in order to determine their eligibility. In some studies, these procedures may not take place unless HIPAA Authorization is obtained OR a waiver of HIPAA Authorization when applicable for the screening procedures is approved by the IRB. [For FDA regulated studies, consent for any screening activities would need to be obtained prior to screening unless specifically waived by the IRB.]

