7.1 Study Design

Describe and explain the study design.

This is a single arm study in which women who are pregnant and participating in the NFP program will be recruited into a study of traditional NFP care with enhanced care focusing on improving CVH throughout the pregnancy and up to 6 months postpartum.

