7.2 Study Procedures

Provide a step by step description of all research procedures being conducted (broken down by visit, if applicable) including such information as below (where and when applicable); describe the following:

- HOW: (e.g., data collection via interviews, focus groups, forms such as surveys and questionnaires, medical/school records, audio/video/digital recordings, photographs, EKG procedures, MRI, mobile

- devices such as electronic tablets/cell phones, observations, collection of specimens, experimental drug/device testing, manipulation of behavior/use of deception, computer games, etc.)
- WHERE: (e.g., classrooms, labs, internet/online, places of business, medical settings, public spaces, etc.)

Intervention Overview. Our pilot CVH intervention will be delivered by NFP visiting nurses starting as early as NFP program enrollment in the first trimester after confirmation of a viable pregnancy and no later than the 28th week of pregnancy and will continue up to 6 months postpartum. The visit schedule will be consistent with the NFP program visit structure to deliver intervention content at regularly scheduled visits that are typically 60 minutes long (weekly visits for the first month following enrollment followed by twice monthly visits until delivery).

The pilot intervention will include a behavioral component aimed at reducing sedentary behaviors as well as utilizing a technology/monitoring component. We will monitor all mothers with a wrist-worn actigraphy device (FitBit) to record activity and sleep, weight scale (Fitbit Scale), intermittent home ambulatory blood pressure self-monitoring (HBPM), and carbon monoxide monitoring administered by the NFP visiting nurse. Carbon monoxide monitoring is part of an attempt to reduce the use of nicotine-containing products. Monitoring with digital devices is discussed below and in the digital device section which follows a description of the interventions. However, the participant will have access to the digital data on the device through smartphone or computer apps to reinforce desired behaviors.

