Study Visit 1 (V1) as summarized in Table 1 will take place at the first home visit after informed consent has been obtained. At this visit, participants will receive “Getting Started” handouts that includes information on setting up the commercially available devices including a 1) a device that monitors physical activity daily for 6 months, 2) a digital scale that monitors weight once per week for 6 months, and 2) a home blood pressure monitor that monitors your blood pressure three times per week for 6 months. NFP visiting nurse will also measure carbon monoxide levels using a provided device at this study visit. During this visit, participants will also be asked to take part in a tobacco cessation program if they have used a nicotine product in the past 3 months. This includes the NFP visiting nurse providing an active referral to a national tobacco quit line and provide a handout on the benefits of and tips for quitting smoking during and or after pregnancy.

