7.3 Duration of Participation

Describe how long subjects will be involved in this research study. Include the number of sessions and the duration of each session - consider the total number of minutes, hours, days, months, years, etc.

Participation in this study will take about 6 months. It is anticipated that Visit 1 will last approximately 45 minutes, 15 minutes for the questions and 30 minutes to instruct in the use of the devices. This may be divided among consecutive visits based on standard care.

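### The primary endpoint runs to 6 months after delivery, but stated participation ends about 6 months after an entry in pregnancy, and no study visit or survey is tied to delivery

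*Combined protocol and SAP*

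**What the plan says.** Several sections promise postpartum coverage:

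- Section 1.2, first primary endpoint: "Successful integration of CVH modules into NFP program during pregnancy and up to 6 months after delivery".
- Section 7.1 describes enhanced care aimed at "improving CVH throughout the pregnancy and up to 6 months postpartum".
- Section 7.2 has nurse delivery starting "no later than the 28th week of pregnancy and will continue up to 6 months postpartum", and as early as the first trimester.
- Section 2.1 offers the transition as novel data: "This study will also monitor blood pressure across the transition from pregnancy to postpartum".
- Section 1.3 lists home blood pressure monitoring after as well as during pregnancy. Aim 2 in section 1.1 covers fidelity of delivery to postpartum women.

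The schedule is anchored on entry instead:

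- Section 4.2.3: "Potential participants will be recruited during pregnancy", before 28 weeks.
- Section 7.2.1: Visit 1 (V1) "will take place at the first home visit after informed consent has been obtained". Devices are set up then, including "a home blood pressure monitor that monitors your blood pressure three times per week for 6 months"; the activity device and scale have the same duration.
- Section 7.3: "Participation in this study will take about 6 months".
- Sections 7.2.2 and 7.2.3 place V2 at 1 to 2 months and V3 at 3 to 4 months after V1. Section 7.2 puts the follow-up questionnaire after V3, without a date. Section 13.0 pays for the last visit and follow-up survey as the third of three payments, so V3 is the last study visit described.
- Table 1 labels V3 as plus 2 months without saying from what. It assigns the satisfaction measure to V3.

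**The concern.** If follow-up lasts about 6 months from a start in pregnancy, the later part of the endpoint window has no stated study collection for anyone, and early entrants may contribute nothing after delivery. Four things are affected:

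- The postpartum half of the integration endpoint would rest on nurse session records alone, with no stated end date.
- Postpartum fidelity, home blood pressure monitoring after pregnancy, and the transition data would come only from women who enter late enough.
- V3 carries both the after-pregnancy activity handout and the satisfaction measure. Giving the handout before birth is not itself an error, but satisfaction, which informs a primary endpoint, could then be rated before the postpartum content has been used.
- Section 8.3 plans descriptive statistics with no split between pregnancy and postpartum. With 20 women (section 8.1), a small postpartum denominator could go unnoticed.

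Nurse acceptability and the consent endpoint are not affected. Actigraphy is limited mainly for another reason: section 7.2 says Fitbit data are not collected as research data.

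**Working it through.** The plan gives no calculation to reproduce, so this is calendar arithmetic.

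**Inputs from the protocol.** V1 is in pregnancy, from the first trimester to about week 28. Participation and device use last 6 months. V3 is 3 to 4 months after V1. Section 2.1 has Nurse-Family Partnership (NFP) visits weekly for 6 weeks after birth, then twice monthly.

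**Assumptions.** Birth at 40 weeks, with 37 and 42 as the range. Entry at weeks 8 to 28 is illustrative, because no entry distribution is given. One month is 4.348 weeks, so 6 months is 26.09 weeks.

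**General result.** Postpartum time observed = 6 months − (time from V1 to birth). This is below 6 months whenever V1 precedes birth, whatever the assumptions.

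**By entry week.** Postpartum weeks = entry week + 26.09 − birth week. For entry at week 28 and birth at 40: 28 + 26.09 − 40 = 14.09 weeks, or 14.09 / 4.348 = 3.24 months. That is 54% of the 26.09-week window.

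| V1 week | Postpartum weeks, birth at 37 | birth at 40 | birth at 42 | NFP postpartum visits inside 6 months (birth at 40) |
|---|---|---|---|---|
| 8 | none | none (ends at week 34.1) | none | 0 |
| 14 | 3.1 | 0.1 | none | 0 |
| 20 | 9.1 | 6.1 | 4.1 | 6 |
| 24 | 13.1 | 10.1 | 8.1 | 7 |
| 28 | 17.1 (3.9 months) | 14.1 (3.2 months) | 12.1 (2.8 months) | 9 |

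The last column counts 6 weekly visits, then one every 2.17 weeks. For week 28 that is 6 + floor(8.09 / 2.17) = 9. The full 6-month window holds 6 + floor(20.09 / 2.17) = 15.

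**Entry week below which no postpartum time is observed.** Birth week − 26.09 = 10.9, 13.9 and 15.9 for births at 37, 40 and 42 weeks.

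**Favourable extremes.** A birth at 32 weeks with week-28 entry gives 28 + 26.09 − 32 = 22.1 weeks (5.1 months). If V1 slips to week 30, a 40-week birth gives 16.1 weeks (3.7 months). Both are still short of 6 months.

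**Where V3 falls.** V3 follows birth only if the entry week exceeds birth week minus the V3 interval. With a 40-week birth this is 40 − 13.04 = 27.0 (V3 at 3 months) or 40 − 17.39 = 22.6 (at 4 months). With a 37-week birth it is 24.0 or 19.6.

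**Table 1.** Counted from V2, plus 2 months gives 1 to 2 months + 2 = 3 to 4 months, which agrees with section 7.2.3. Counted from entry it disagrees, and V3 for week-28 entry would fall at 28 + 8.70 = 36.7 weeks.

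**The case against.** The strongest reply is that integration is a property of delivery, not of participant follow-up. Nurses deliver content at ordinary NFP visits, which section 2.1 says continue until the infant is 21 months old. Section 7.2 has nurses documenting each session, with no end date. The endpoint could therefore be measured from those records after participation ends. This stands in part: nothing stops the records, but nothing says they continue as study data once a woman's 6 months are over. Nor would they supply participant-side data such as satisfaction or blood pressure logs.

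Second, the windows say up to 6 months, and participation is only approximate. An upper bound does tolerate shorter individual follow-up. But for week-28 entry the shortfall is 6 − 3.2 = 2.8 months with a 40-week birth (2.1 to 3.2 months for births at 37 to 42 weeks), which rounding does not explain, and earlier entrants fall further short.

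Third, Table 1 is headed as prenatal and/or postpartum, some content adapts to delivery (activity guidance and blood pressure alerts), and entry-anchored visits are a legitimate choice in a small descriptive pilot. That is fair. The fault lies in claiming a window that the chosen schedule does not observe.

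Fourth, because the follow-up packet has no date, satisfaction might be collected later than V3. That is possible, and it is why the date needs stating. The Table 1 label likewise needs only clarification, since one reading is consistent.

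**Conclusion.** The concern holds. As written, no woman whose V1 is in pregnancy can be followed to 6 months postpartum within the stated participation period. With a 40-week birth, follow-up reaches at most about 3.2 months postpartum for week-28 entry and does not reach delivery for entry before about week 13.9. The shortfall itself does not depend on the assumed birth or entry weeks; its size does. No proportion of women affected can be given, because the protocol states no entry-week distribution. It remains open whether nurse session records extend beyond participation. This should be fixed, since one primary endpoint and the postpartum blood pressure endpoint claim more than the schedule delivers, but it does not undermine the whole pilot.

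**What to change.** Reconcile sections 1.2, 2.1, 7.1, 7.2 (with Table 1), 7.2.1, 7.2.3 and 7.3 to one timeline. State what plus 2 months counts from, date the follow-up survey, and say whether nurse session records continue as study data after participation ends. Then choose one option:

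- **(a) Anchor on delivery.** Tie the last study assessment and the satisfaction and follow-up survey to an existing NFP visit after birth, such as one of the weekly visits in the first 6 weeks, and state whether device monitoring is extended to match. If that visit is earlier than 6 months postpartum, narrow section 1.2 accordingly.
- **(b) Keep entry-anchored visits.** Restate sections 1.2 and 7.1 to claim only the postpartum period observed.

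Under either option, record gestational or postpartum week at each contact. Report pregnancy and postpartum data separately, with the number of women in each.

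**Cost.** Both options need a protocol amendment; (b) costs only a narrower claim. For (a) with the last assessment at 6 weeks postpartum and a 40-week birth, participation lasts (46 − entry week) / 4.348 months: 4.1, 6.0, 7.4 and 8.7 months for entry at weeks 28, 20, 14 and 8. Only entry before about week 20 goes beyond the stated 6 months. If the roughly 12-month pilot period in section 3.3.2 covers enrolment and follow-up together, women would have to enter by month 12 − 4.14 = 7.9 (week-28 entry) down to month 12 − 8.74 = 3.3 (week-8 entry).

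Covering the full 6 months postpartum needs (40 − entry week) / 4.348 + 6 months: 8.8 months for week 28 and 13.4 for week 8. That exceeds 12 months for entry before week 13.9.

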3.3.2 Follow-up for withdrawn subjects

Describe when and how to withdraw subjects from the study; the type and timing of the data to be collected for withdrawal of subjects; whether and how subjects are to be replaced; the follow-up for subjects withdrawn from investigational treatment.

Participants may withdraw consent at any time, we will utilize all data collected up to that point. As time allows (~12 month pilot period maximum), we will recruit additional participants for the pilot.

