8.0 Number of Subject and Statistical Plan

8.1 Number of Subjects

Indicate the maximum number of subjects to be accrued/enrolled. Distinguish between the number of subjects who are expected to be enrolled and screened, and the number of subjects needed to complete the research procedures if applicable (i.e., numbers of subjects excluding screen failures.)

We anticipate enrolling 20 pregnant women for this pilot study.

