8.2 Sample size determination

If applicable, provide a justification of the sample size outlined in section 8.1 to include reflections on, or calculations of, the power of the study.

Because this is a pilot study, no formal sample size calculations were completed.

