11.2 Potential Benefits to Others

Include benefits to society or others.

The results of the research will help scientists to better understand the feasibility and acceptability of delivering enhanced intervention content during NFP program home visits. Understanding these factors will help scientists designed a large scale, multi-site trial designed to improve CVH for women and infants.

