15.2 Feasibility of recruiting the required number of subjects

Indicate the number of potential subjects to which the PSU study team has access. Indicate the percentage of those potential subjects needed for recruitment.

Given the small sample size for this pilot study, it is feasible to recruit the number of subjects needed. Our two NFP agency partners enroll several hundred pregnant women into their programs annually. The Center for Childhood Obesity Research (CCOR) has previous experience recruiting pregnant women and women who have recently delivered and has long standing working relationship with Geisinger and UPMC offices across the state.

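### The enrolment endpoint is a count of 20 with no denominator, rate or recruitment window, so it could be met even if most eligible women decline

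*Combined protocol and SAP*

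**What the plan says.** Aim 3 in section 1.1 is "To demonstrate the feasibility of enrolling and following pregnant women participating in the NFP program into a pilot research study". Of the three primary endpoints in 1.2, only the third concerns enrolment: "Successful consent of 20 pregnant women into pilot study". Section 8.1 gives the same number as the plan for accrual: "We anticipate enrolling 20 pregnant women for this pilot study". Section 8.2 gives no basis for it: "Because this is a pilot study, no formal sample size calculations were completed".

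On the source population, 15.2 states: "Our two NFP agency partners enroll several hundred pregnant women into their programs annually". The template prompt there asks what percentage of potential subjects is needed. The answer gives no percentage and argues from size: "Given the small sample size for this pilot study, it is feasible to recruit the number of subjects needed".

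The only time limit is in 3.3.2, where it concerns recruitment after withdrawals: "As time allows (~12 month pilot period maximum), we will recruit additional participants for the pilot". The endpoint does not refer to it.

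Section 8.3 lists recruitment among the feasibility items to be described, without a denominator or criterion. Section 4.2.4 confines screening information to the eligibility decision and keeps it out of research analyses. Section 11.2 states what the results are for: "Understanding these factors will help scientists designed a large scale, multi-site trial designed to improve CVH for women and infants".

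**The concern.** The success rule has one input, the number of consents. The number of women who could have consented, or were asked, does not enter it. Because the threshold is the accrual target, completing accrual is itself the success.

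A multi-site trial is planned from the uptake rate. If 80% of eligible women agree, 25 must be asked to enrol 20. If 10% agree, 200 must be asked, which is eight times as many. That changes the number of agencies, the length of accrual and how far those enrolled represent the programme. Once 20 women have consented, the endpoint reports both cases as successful. If the denominator is not recorded, or 4.2.4 is read as barring its use, the pilot ends without the figure it was meant to supply.

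**Working it through.** **The plan's own figure.** The threshold is 20 (1.2), equal to the planned enrolment (8.1). There is no calculation to reproduce, since 8.2 says none was done.

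**Inputs.** Let N be the number of eligible women actually offered the study. The documents do not give N. It would be annual NFP enrolments × fraction of a year open to recruitment × fraction eligible × fraction approached. Only the first factor is described (several hundred, 15.2). The rest is assumed below, and consent decisions are treated as independent.

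**Step 1: refusal compatible with the endpoint.** Declines tolerated = 1 − 20/N. For N = 200, 1 − 20/200 = 90%. For N = 50, 1 − 20/50 = 60%.

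**Step 2: chance of meeting the count.** P(X ≥ 20), with X binomial (N, p) and p the true consent rate.

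| N offered | 20/N (exact 95% CI) | Declines tolerated | P at p = 10% | P at p = 30% | P at p = 50% |
|---|---|---|---|---|---|
| 25 | 80% (59–93%) | 20% | <0.001 | <0.001 | 0.002 |
| 50 | 40% (26–55%) | 60% | <0.001 | 0.085 | 0.941 |
| 100 | 20% (13–29%) | 80% | 0.002 | 0.991 | >0.99 |
| 200 | 10% (6–15%) | 90% | 0.534 | >0.99 | >0.99 |
| 300 | 6.7% (4–10%) | 93.3% | 0.983 | >0.99 | >0.99 |
| 400 | 5% (3–8%) | 95% | >0.99 | >0.99 | >0.99 |

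The consent rate at which the rule is met half the time is 39% for N = 50, 20% for 100, 9.8% for 200 and 6.5% for 300. At a true rate of 10%, 234 women must be offered the study for an 80% chance of reaching 20, and 256 for a 90% chance.

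**Step 3: how the pool might shrink.** All fractions are assumed.

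- 300 enrolments, 12 months, 70% eligible, all approached: 300 × 0.7 = 210; declines tolerated 1 − 20/210 = 90.5%.
- The same over 6 months: 105; 81.0%.
- The same with half approached: about 52; 61.5%.
- 200 enrolments, 6 months, 50% eligible, half approached: 200 × 0.5 × 0.5 × 0.5 = 25; 20%.

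**Step 4: what a rate would add.** The same 20 consents could be 20/25 = 80% (59–93%), 20/40 = 50% (34–66%) or 20/200 = 10% (6–15%). Even at this sample size the interval for 10% is clear of the other two. The count cannot show that difference.

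**The case against.** The strongest objection is to the size of the effect. A reader might infer from 15.2 that the endpoint is met even if nine in ten eligible women refuse. The documents do not support that as a general statement. Section 15.2 counts programme enrolments, not eligible women or women offered the study. Aim 2 trains only selected nurses, sections 3.1 and 3.2 add criteria for age, language, internet and smartphone access, and others, and participation of about 6 months (7.3) inside a pilot of about 12 months may shorten recruitment. At a 10% consent rate the chance of reaching 20 is 0.534 with 200 women and only 0.002 with 100. A large eligible share is plausible, because 2.1 describes NFP as serving first-time mothers who enrol by week 28, but no share is stated.

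A reader might also infer that the endpoint cannot separate feasible from infeasible enrolment at all. That goes too far: failing to reach 20 within the pilot period would be informative, and with a small pool the count does discriminate. It can also be said that 8.3 already covers recruitment and that a 20-woman descriptive pilot needs no pass mark. Both are fair in part. However, 8.3 defines no denominator, and 4.2.4 may withhold one.

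The objection also limits the remedy. Dividing consents by caseload would mix women never asked and ineligible women with refusals. With 200 on the caseload, 25 eligible and asked, and 20 agreeing, caseload gives 10%, while willingness is 80%.

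**Conclusion.** The point holds in a conditional form. The third primary endpoint is a count equal to the planned sample size, with no denominator, rate or window, and it could be met even if most eligible women decline. The size depends on N: about 90% if 200 or more eligible women are offered the study, about 60% with 50, and 20% with 25. N is an assumption throughout.

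Uncertainty about N does not rescue the endpoint. Because N is neither fixed nor planned to be recorded, reaching 20 cannot be converted into a consent rate, and under 8.3 and 4.2.4 as written that rate may not be recoverable. This is worth correcting before enrolment starts. It does not make the pilot uninformative, since a shortfall would still count against feasibility.

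**What to change.** In 8.1, keep 20 as the accrual target. In 1.2 and 8.3, define the enrolment-feasibility endpoint as women giving written informed consent divided by eligible women approached, by agency and overall, with an exact 95% CI, and add the calendar time from first to 20th consent.

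Have the recruiting nurses keep aggregate, non-identifying tallies of women identified, approached, eligible and consented, and amend 4.2.4 to allow these counts in the analysis. Since 4.2.4 takes verbal agreement before any screening question, a woman who declines at that step has unknown eligibility. Report the approached count alongside the rate so that she stays visible.

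Report the caseload count of women under 28 weeks and aged 18 or over separately, as reach and not as the consent rate. A minimum rate stated in advance is optional.

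The cost is a short tally by the nurses, wording changes in three sections, and a figure that may look less favourable than a met target. No extra participants or study visits are needed.
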